4.1.4.6 Rationale for Biomarker Discovery in Patients with Leptomeningeal Disease

Response to therapy in patients with LMD has been historically difficult to assess. In randomized trials, radiologic response has been assessed by contrast-enhanced MRI scans, and CSF response by clearance of initially positive CSF cytology⁶⁷. However, novel genomic biomarkers of tumor burden have been identified in recent years include circulating tumor DNA (ctDNA) in the plasma⁶⁸⁻⁷⁰ and in anatomically-relevant fluids such as sputum in lung cancer patients⁷¹ and endocervical fluid in ovarian/cervix cancer patients⁷². Furthermore, [name], [name] and colleagues at JHH were able to detect appreciable levels of tDNA in the CSF of patients with primary brain tumors, which was more sensitive for tumors that abutted a CSF reservoir, and in high-grade tumors^{73,74}. In addition, it has been shown that the presence of an effector T-cell population in solid tumors^{74,75}, and the expression of immune checkpoint markers such as PD-L1 in infiltrating tumor and immune cells in the tumor microenvironment, correlates with prognosis and response to anti-PD-1 therapy in solid tumors including NSCLC²⁰ and other solid tumors⁷⁶. The tumor microenvironment in patients with LMD is the CSF, and an assessment of the genomic and immunologic landscape of tumor cells/tDNA and immune cells present in the CSF has not been previously described. Since

LMD is in direct contact with CSF reservoirs, this may represent a population of patients in which to assess for the presence of CSF t-DNA, and if detectable, potentially expand its use to quantify tumor burden and measure response to therapy in these patients.

4.1.4.7 Rationale for Dose Selection/Regimen/Modification

An open-label Phase I trial (Protocol 001) was conducted to evaluate the safety and clinical activity of single agent MK-3475. The dose escalation portion of this trial evaluated three dose levels, 1 mg/kg, 3 mg/kg, and 10 mg/kg, administered every 2 weeks (Q2W) in subjects with advanced solid tumors. All three dose levels were well tolerated and no dose-limiting toxicities were observed. This first in human study of MK-3475 showed evidence of target engagement and objective evidence of tumor size reduction at all dose levels (1 mg/kg, 3 mg/kg and 10 mg/kg Q2W). No MTD has been identified to date. 10.0 mg/kg Q2W, the highest dose tested in PN001, will be the dose and schedule utilized in Cohorts A, B, C and D of this protocol to test for initial tumor activity. Recent data from other clinical studies within the MK-3475 program has shown that a lower dose of MK-3475 and a less frequent schedule may be sufficient for target engagement and clinical activity.

PK data analysis of MK-3475 administered Q2W and Q3W showed slow systemic clearance, limited volume of distribution, and a long half-life (refer to IB). Pharmacodynamic data (IL-2 release assay) suggested that peripheral target engagement is durable (>21 days). This early PK and pharmacodynamic data provides scientific rationale for testing a Q2W and Q3W dosing schedule.

A population pharmacokinetic analysis has been performed using serum concentration time data from 476 patients. Within the resulting population PK model, clearance and volume parameters of MK-3475 were found to be dependent on body weight. The relationship between clearance and body weight, with an allometric exponent of 0.59, is within the range observed for other antibodies and would support both body weight normalized dosing or a fixed dose across all body weights. MK-3475 has been found to have a wide therapeutic range based on the melanoma indication. The differences in exposure for a 200 mg fixed dose regimen relative to a 2 mg/kg Q3W body weight based regimen are anticipated to remain well within the established exposure margins of 0.5 – 5.0 for MK-3475 in the melanoma indication. The exposure margins are based on the notion of similar efficacy and safety in melanoma at 10 mg/kg Q3W vs. the proposed dose regimen of 2 mg/kg Q3W (i.e. 5-fold higher dose and exposure). The population PK evaluation revealed that there was no significant impact of tumor burden on exposure. In addition, exposure was similar between the NSCLC and melanoma indications. Therefore, there are no anticipated changes in exposure between different indication settings.

The rationale for further exploration of 2 mg/kg and comparable doses of pembrolizumab in solid tumors is based on: 1) similar efficacy and safety of pembrolizumab when dosed at either 2 mg/kg or 10 mg/kg Q3W in melanoma patients, 2) the flat exposure-response relationships of pembrolizumab for both efficacy and safety in the dose ranges of 2 mg/kg Q3W to 10 mg/kg Q3W, 3) the lack of effect of tumor burden or indication on distribution behavior of pembrolizumab (as assessed by the population PK model) and 4) the assumption that the dynamics of pembrolizumab target engagement will not vary meaningfully with tumor type.

The choice of the 200 mg Q3W as an appropriate dose for the switch to fixed dosing is based on simulations performed using the population PK model of pembrolizumab showing that the fixed dose of 200 mg every 3 weeks will provide exposures that 1) are optimally consistent with those obtained with the 2 mg/kg dose every 3 weeks, 2) will maintain individual patient exposures in the exposure range established in melanoma as associated with maximal efficacy response and 3) will maintain individual patients exposure in the exposure range established in melanoma that are well tolerated and safe.

A fixed dose regimen will simplify the dosing regimen to be more convenient for physicians and to reduce potential for dosing errors. A fixed dosing scheme will also reduce complexity in the logistical chain at treatment facilities and reduce wastage.

4.1.5 Rationale for Endpoints

Immune checkpoint blockade has demonstrated benefit in patients with parenchymal BM, but has not been studied in LMD. This study will provide an underserved group of patients with a treatment option that may benefit them. In addition, next-generation genomic and immunologic studies from CSF and serum may uncover new biomarkers in LMD.

4.1.5.1 Efficacy Endpoints

4.1.5.1.1 Primary Endpoint:

The primary efficacy endpoint is to evaluate CNS response with pembrolizumab in patients with LMD from solid tumors. CNS response will be defined either as radiologic response, cytologic response, or clinical response, whichever is easier to assess. Radiologic response will be defined as a reduction in size of a measurable lesion on a contrast-enhanced MRI scan of the brain. Cytologic response will be defined as a negative CSF cytology result in 2 consecutive samples, in patients who have initial positive cytology prior to treatment, or a clinical response, defined as an improvement in objective neurologic signs or symptoms attributable to LMD (Table 8). Response assessment is detailed in section 6.1.2.7.

4.1.5.1.2 Secondary Endpoints:

- **1. CNS Progression-free Survival:** A secondary endpoint of this study is to evaluate CNS-PFS, which will be defined as the time from study enrollment until CNS progression (radiologic, cytologic or clinical), or death, whichever occurs first. CNS progression will be classified as radiologic (determined by contrast-enhanced MRI scan), cytologic (determined by pathologic assessment of CSF cytology including cell count, differential, glucose) or clinical progression (defined as new objective neurologic signs or symptoms, attributable to LMD), as detailed in section 6.1.2.7.
- 2. **Overall Survival:** A secondary endpoint of this study is to evaluate OS, which will be defined as the time from study enrollment until death from any cause. Deaths from progressive disease will be stratified as related to CNS progression, related to systemic progression, or both.

8A

3. **Safety:** Safety will be evaluated according to the National Cancer Institute Common Terminology Criteria for Adverse Events (NCI CTCAE) version 4.0^{27} safety will be determined by the number of treatment-related toxicities of > grade 3 severity by CTCAE Version 4.0.

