After completion of 4 cycles of therapy, subjects will be evaluated every 6-9 weeks with radiologic imaging of the body (CT) and CNS (MRI) to assess response to treatment both inside and outside of the CNS. Response assessments will be completed by a radiologist at the treating site, findings will be confirmed by an independent radiologist, and evaluated by RECIST 1.1 criteria and immune-related criteria (irRC) for systemic disease, and MRI criteria for CNS disease. Following the first radiologic assessment of the body that demonstrates radiologic progressive disease (PD), RECIST 1.1 will be adapted as described in section 6.1.2.7.5 (Table 9) to accommodate for the tumor response patterns seen with pembrolizumab treatment (e.g., tumor flare) using immune-related RECIST criteria. Contrast-enhanced MRI Brain scans will be used to assess for measurable disease in the CNS at the time of screening, and to determine CNS radiologic response during the study. CNS radiologic response by MRI will be defined as a reduction in size of a measurable lesion throughout the neuro-axis, where a measurable lesion will be defined as one that is greater than or equal to 3mm in size, as detailed in section 6.1.2.7. CNS cytologic response will be assessed by two serial CSF cytology samples, as detailed in the section 6.1.2.8.3. Clinical response will be evaluated by the treating investigator, detailed in section 6.1.2.7 (Table 8).

[figure not shown]
After completion of 4 cycles of therapy or the patient's last dose of therapy, each subject will be followed for 90 days after the end of treatment for adverse event monitoring, or 30 days after the end of treatment if the subject initiates new anti-cancer therapy. Subjects who discontinue treatment for reasons other than PD will have post-treatment follow-up for disease status until PD, initiation of a new cancer therapy, withdrawal of consent, or becoming lost to follow-up. All subjects will be followed by telephone contact for overall survival (OS) until death, withdrawal of consent or the Investigator is notified by the Sponsor to discontinue follow-up, whichever comes first.

This trial will be conducted in conformance with Good Clinical Practices.

Specific procedures to be performed during the trial, as well as their prescribed times and associated visit windows, are outlined in the Trial Flow Chart – Section 5.0 Details of each procedure are provided in Trial Procedures- Section 6.0.

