A limited number of prospective studies have been completed in patients with solid tumors and LMD. Most recently a phase II study of single agent temozolamide demonstrated a

needed

response rate of 15.8% $(n=3/19)^{55}$, and single agent pemetrexed, 4% (n=1/21), in all solid tumors⁵⁶ (Table 1).

Patients with areas of bulky LMD that cause obstruction of CSF flow or are thought to be causing neurologic deficit, may be treated with local radiation therapy (RT) or WBRT for palliation (Figure 1). There are no prospective clinical studies evaluating the use of local RT or WBRT alone, however the Southwest Oncology Group (SWOG) investigated the combination of WBRT and IT-MTX in solid tumors in 1988⁵⁷ (Table 1).

Interpretation of clinical studies in patients with LMD are complicated by a lack of randomized data, and a variety of response assessments used in reported studies. In the studies detailed in Table 1 below, response may have been captured as clinical response, radiologic response, or cytologic response, or a combination of two or three of these response assessments, defined in different ways. Definitions for clinical response on these studies included: improvement or stability in neurologic symptoms^{34,58}, improvement in neurologic function and KPS at 1 month³⁵, or improvement in neurologic function with cessation of steroid use⁵⁵. Definitions for radiologic response in these studies included: reduction in size of measurable lesions on brain MRI^{36,55}, CT brain or myelogram³¹; and definitions for cytologic response may have referred to clearance of previously positive CSF cytology at 1 month³⁵, or on 2 or more consecutive CSF samples³⁴. In one study, response was defined by clinical, radiologic and cytologic parameters, such that a complete responder would demonstrate a normal neurologic examination, negative CSF cytology, normal CSF protein and glucose, and no measurable disease on CT or myelogram³¹. In a second study, response was defined by clinical and cytologic parameters, with the combination of a negative CSF cytology assessment and stable/improved neurologic function as response³². Additionally, selected studies included patients with both LMD and parenchymal brain metastases, which may confound the interpretation of some response data^{36,56}. Therefore, historical data of response rates in patients with LMD are subject to wide variability and interpretation.

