4.3.3 Trial Blinding/Masking

This is an open-label trial; therefore, the Sponsor, investigator and subject will know the treatment administered.

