4.6.1 Acceptable Concomitant Medications

All treatments that the investigator considers necessary for a subject's welfare may be administered at the discretion of the investigator in keeping with the community standards of medical care. All concomitant medication will be recorded on the case report form (CRF) including all prescription, over-the-counter (OTC), herbal supplements, and IV medications

and fluids. If changes occur during the trial period, documentation of drug dosage, frequency, route, and date may also be included on the CRF.

Palliative and supportive care is permitted during the course of this trial for underlying medical conditions and the management of symptoms. Major surgery for tumor control or symptom management is not permitted during the study or within 3 weeks of study commencement, as outlined in section 4.2.7. Palliative radiotherapy is permitted if considered medically necessary by the treating physician as long as the lesion is not the patient's sole measurable lesion on brain or spine MRI or a defined target lesion in the body by RECIST 1.1, as detailed in section 4.2.6. Trial therapy should be held during the course of palliative radiation, and should be resumed no early than the next schedules dose of trial therapy. The specifics of the radiation treatment given, including location, will be recorded. Additionally, patients who receive radiation therapy will be analyzed separately to assess the potential impact of radiation therapy on clinical outcomes.

All concomitant medications received within 28 days before the first dose of trial treatment and 30 days after the last dose of trial treatment should be recorded. Concomitant medications administered after 30 days after the last dose of trial treatment should be recorded for SAEs and ECIs as defined in Section 6.2.

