7.2.4 Primary Efficacy Endpoint

CNS response

CNS response rate is defined as the proportion of the subjects in the analysis population who have a radiologic reduction in size of measurable CNS tumor lesions on an MRI brain scan, develop clearance of positive CSF cytology on 2 consecutive CSF specimens after an initial positive specimen has been obtained, or an improvement in neurologic function, as detailed in Table 8. In patients with more than one available response criterion, the most easily assessable criterion will be used.

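### A clinical-only CNS response is judged by the unblinded treating investigator with no account of steroid dose, so some steroid-related improvement can still be counted as a primary response

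*Combined protocol and SAP*

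**What the plan says.** **Definition.** Section 4.1.5.1.1 accepts a radiologic response, a cytologic response, "or a clinical response, defined as an improvement in objective neurologic signs or symptoms attributable to LMD". Section 7.2.4 lists the same three routes and ends with "or an improvement in neurologic function, as detailed in Table 8". Table 8 (section 6.1.2.7) rates improved neurologic function with stable MRI or CSF as *Improved* overall. It rates improved function with MRI or CSF progression as *Progression*.

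**Who judges it.** Section 2.1: "Clinical response will be evaluated by the treating investigator". Section 4.3.3 says that "the Sponsor, investigator and subject will know the treatment administered". For imaging, section 2.1 adds that "findings will be confirmed by an independent radiologist". Cytologic response needs two consecutive negative samples.

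**Steroids.**
- Inclusion criterion 6 admits patients on a non-escalating steroid requirement for CNS symptoms. Exclusion criterion 2 caps systemic steroids at 10 mg prednisone per day in the 7 days before first dose.
- Section 4.6.2 prohibits systemic glucocorticoids during screening and treatment. The exceptions are suspected immune-related events of clinical interest and physiologic doses after consultation. Patients who need a prohibited therapy should be removed from the trial.
- Section 4.7.1 directs corticosteroids for several immune-related toxicities, mostly with tapers of at least 4 weeks.
- Section 4.6.1 states: "All treatments that the investigator considers necessary for a subject's welfare may be administered at the discretion of the investigator". It requires concomitant medications to be recorded, but leaves documentation of dose changes optional.

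**Precedent.** Among the earlier clinical-response definitions that section 4.1.4.4 lists, one is "improvement in neurologic function with cessation of steroid use".

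**The concern.** Steroids can improve neurologic symptoms by themselves. If a patient's steroid dose is higher at the response assessment than at first dose, neurologic improvement cannot be attributed cleanly to pembrolizumab, yet the endpoint as written would count it.

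The clinical component is also the least protected of the three: it has neither a second reader nor a confirmatory assessment. Section 7.2.4 adds that, where several criteria are available, the one easiest to assess is used, which can steer classification towards it.

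The result is a single response rate with no control arm, so a misattributed response would not show in the data. The plan analyses irradiated patients separately (section 4.6.1) but has no parallel analysis for steroid use, and it plans neither a rate by component nor a radiologic-or-cytologic rate.

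**Working it through.** **1. The plan's own figures.** Section 7.2.1 uses 16 analyzable patients and 10% loss: 16/0.9 = 17.8, rounded up to 18, as stated. Its table gives two-sided 90% Clopper-Pearson limits at N = 16. For x responders the limits are the α/2 quantile of Beta(x, 17−x) and the 1−α/2 quantile of Beta(x+1, 16−x). This returns 2.3–34.4% for 2/16, 5.3–41.7% for 3/16 and 9.0–48.4% for 4/16, all as printed. Eleven of the 12 limits match; the upper limit for 6/16 is printed as 60.1% and computes to 60.9%, which has no bearing here.

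**2. Is there a steroid condition in any response definition?** Sections 2.1, 4.1.5.1.1, 6.1.2.7 (with Table 8) and 7.2.4 contain none.

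**3. Which routes stay open under the steroid restrictions?**
- *Raising steroids for LMD symptoms:* barred by 4.6.2.
- *Stable steroids at entry:* limited by inclusion 6 and exclusion 2. An unchanged dose does not explain improvement from baseline.
- *Immune-event courses:* allowed by 4.6.2 and directed by 4.7.1. A taper of at least 4 weeks is longer than one 3-week cycle. For several toxicities Table 5 requires discontinuation only if steroids cannot be brought to 10 mg prednisone or less within 12 weeks. The endpoint is read at 12 weeks, so overlap is possible.
- *Investigator discretion in 4.6.1:* open on its wording, though 4.6.2 follows with the specific prohibition.
- *Removal for needing steroids:* the analysis population is all eligible patients with at least one dose (Table 12). Such a patient stays in it, and nothing states that the patient is a non-responder.

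**4. Size per response.** 1/16 = 6.25 percentage points. Table 12 names 95% exact intervals for reporting, so those are used below. The number misattributed is an assumption.

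| Misattributed (assumed) | Counted | Rate | 95% exact CI |
|---|---|---|---|
| 0 | 2/16 | 12.5% | 1.55–38.35% |
| 1 | 3/16 | 18.8% | 4.05–45.65% |
| 2 | 4/16 | 25.0% | 7.27–52.38% |

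**5. Sensitivity.** Let p be the true response rate and s the share of true non-responders counted through steroid-related improvement. The counted rate is q = p + (1−p)s, and the number counted is Binomial(16, q). The documents give neither p nor s. Four of 16 is used only to show scale; it is not a threshold in the plan.

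| P(at least 4 of 16 counted) | s = 0 | s = 5% | s = 10% | s = 20% |
|---|---|---|---|---|
| p = 5% | 0.007 | 0.06 | 0.19 | 0.56 |
| p = 10% | 0.07 | 0.19 | 0.36 | 0.70 |

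At p = 10% the expected number misattributed is 16 × 0.9 × s: 0.72 at s = 5%, 1.44 at 10% and 2.88 at 20%.

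**The case against.** The strongest reply is that the protocol already controls steroids. Section 4.6.2 bars the obvious route, which is raising steroids to treat LMD symptoms, and entry doses are capped and non-escalating. The immune-event exception and the 4.7.1 guidance are largely one route, not two. The discretion in 4.6.1 is general, and a specific prohibition would normally be read as limiting it. This stands: what remains is mainly an immune-event course that happens to coincide with the assessment.

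There are also partial safeguards. The definition asks for objective signs or symptoms attributable to LMD, and Table 8 overrides clinical improvement when MRI or CSF progresses. Neither helps when imaging and cytology are stable, which is the case at issue.

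Section 4.1.4.4 shows varied practice. Only one of its listed clinical definitions has a steroid condition, so it shows that the issue was known, not that a standard was ignored. Unblinded assessment is inherent in a single-arm open-label design. The plan is estimation-only, so no decision threshold is crossed.

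A reader might infer that steroid use is uncontrolled and that steroid-driven improvement will routinely be credited to pembrolizumab. The restrictions above do not support that. Nor do the documents support reading the doubling from 2/16 to 4/16 as an expected bias; it is the upper end of an assumed range.

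**Conclusion.** The point holds in a limited form. Neurologic improvement alone, judged by an unblinded investigator without confirmation, makes a primary response, and no definition accounts for steroid dose. Steroid-related improvement *can* be counted; the documents do not show that it will be, or how often. Each such response moves the rate by 6.25 points. Zero to two of them on top of 2/16 gives 12.5% to 25%, with wide and overlapping intervals. These counts, like p and s, are assumptions. Because the trial has no control arm and no component-level rate, the reported result would not reveal the problem. A low-cost change to the plan is justified.

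Separately, inclusion criterion 6 (non-escalating steroids for CNS symptoms allowed at entry) and section 4.6.2 (systemic glucocorticoids for that purpose prohibited during screening and treatment) contradict each other and must be reconciled.

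**What to change.** For endpoint classification only, with no change to treatment rules:

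1. In 4.1.5.1.1, Table 8 and 7.2.4, count a clinical-only response only if the systemic steroid dose at the assessment is no higher than at first dose. State there the response status of a patient removed under 4.6.2.
2. Make systemic steroid dose at baseline and at each response assessment a required CRF item. The medication review at each cycle does not guarantee it, because 4.6.1 leaves dose documentation optional.
3. In 7.2.4, report the response rate by component, and the radiologic-or-cytologic rate with its exact interval, beside the composite.
4. Reconcile inclusion criterion 6 with 4.6.2.

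Cost: protocol and SAP wording, one CRF item and one table. The sample size stays at 16 analyzable and 18 enrolled. The downside is a possibly lower composite rate, because the rule would also exclude true clinical responders who were on steroids for an immune event. The component table would show how many patients that affects if clinical-only improvements excluded by the rule are listed in it.
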